**Date**: 20 May 2019 **Page 48 of 132** 

## **KRd and KPd Arms**

Female subjects of childbearing potential unwilling to use 2 methods of contraception (1 of which must be highly effective; see Section 12.5) during the study and for an additional 30 days after the last dose of study drug. Additionally, subjects must be using contraception at least 28 days prior to initiating treatment. Refer to Section 12.5 for additional contraceptive information.

253 Female subjects of childbearing potential with a positive serum pregnancy test assessed within 14 days prior to first dose of study drug or a positive urine pregnancy test within 24 hours prior to first dose. In addition, females of childbearing potential must agree to pregnancy testing weekly during the first 4 weeks of pomalidomide or lenalidomide use followed by a pregnancy test every 4 weeks in females with regular menses or every 2 weeks in females with irregular menstrual cycles.

# 6.3 Subject Enrollment

Before subjects begin participation in any study-specific activities/procedures, Amgen requires a copy of the site's written Institutional Review Board (IRB) approval of the protocol, informed consent form (ICF), and all other subject information and/or recruitment material, if applicable (see Section 12.3).

The subject must personally sign and date the IRB and Amgen approved informed consent before commencement of study-specific procedures.

A subject is considered enrolled when the investigator decides that the subject has met all eligibility criteria. The investigator is to document this decision and date, in the subject's medical record and in/on the enrollment case report form (CRF).

Each subject who enters into the screening period for the study (defined as the point when the subject signs the informed consent) receives a unique subject identification number before any study-related activities/procedures are performed. The subject identification number will be assigned via IXRS. This number will be used to identify the subject throughout the clinical study and must be used on all study documentation related to that subject.

The subject identification number must remain constant throughout the entire clinical study; it must not be changed after initial assignment, including if a subject is rescreened.

#### 6.4 Screen Failures

Screen failures are defined as subjects who consent to participate in the clinical study but are not subsequently enrolled in the study. A minimal set of screen failure information will be collected that includes demography, screen failure details, eligibility

Protocol Number: 20170596

**Date:** 20 May 2019 Page 49 of 132

criteria, and any serious adverse events. In the event a screen-failure subject experiences a serious adverse event, medical history and prior therapies will also be collected.

Individuals who do not meet the criteria for participation in this study (screen failure) may be rescreened once. Refer to Section 9.1.1 for more detail.

#### 7. Treatments

Study treatment is defined as any investigational product(s), non-investigational product(s), placebo, or medical device(s) intended to be administered to a study subject according to the study protocol.

Note that in several countries, investigational product and non-investigational product are referred to as investigational medicinal product and non-investigational medicinal product, respectively.

The Investigational Product Instruction Manual (IPIM), a document external to this protocol, contains detailed information regarding the storage, preparation, destruction, and administration of each treatment shown in below.

#### 7.1 Treatment Procedures

# 7.1.1 Investigational Products

# 7.1.1.1 Dosage Formulation

Carfilzomib will be manufactured and packaged by Amgen and distributed using Amgen clinical study drug distribution procedures.

Carfilzomib is supplied as a sterile, lyophilized, white to off-white powder, ready for reconstitution. It is supplied for single use in 50 mL Type 1 glass vials containing 60 mg of carfilzomib drug product with an elastomeric stopper and flip-off lid.

# 7.1.1.2 Dosage, Administration, and Schedule

For all treatment arms, carfilzomib will be administered at 20 mg/m² on days 1 and 2 of the first cycle (see Table 7-1). For subjects in the Kd arm, carfilzomib will be administered at 56 mg/m² on days 8, 9, 15, and 16 of the first cycle, and then on days 1, 2, 8, 9, 15, and 16 in cycle 2. Starting with cycle 3 through cycle 12, carfilzomib will be administered at 70 mg/m² on days 1, 8, and 15 of each 28-day cycle. For subjects in the KRd and KPd arms, carfilzomib will be administered at 27 mg/m² on days 8, 9, 15, and 16 of the first cycle, and then on days 1, 2, 8, 9, 15, and 16 in cycle 2. Starting with cycle 3 through cycle 12, carfilzomib will be administered at 56 mg/m² on days 1, 8, and 15 of each 28-day cycle.

Protocol Number: 20170596

**Date:** 20 May 2019 Page 50 of 132

At the time of implementation of protocol amendment 3, subjects previously enrolled may have completed more than 2 but less than 6 cycles of twice weekly carfilzomib dosing on the Kd arm as per protocol amendment 2. These subjects should complete the dosing regimen as per protocol amendment 2, (ie, 6 cycles of twice weekly dosing for carfilzomib [Kd 56 mg/m²] transitioning to once weekly dosing for carfilzomib [Kd 70 mg/m²], starting with cycle 7). For these subjects, the schedule of activities outlined per Table 2-1 for cycles 1 and 2 will continue for cycles 1 through 6. At the start of cycle 7, these subjects will then follow the schedule of activities as outlined per Table 2-1 cycles 3 through 12. In addition, the starting nominal dose of carfilzomib on day 1 cycle 7 (which is the initiation of the once weekly carfilzomib dosing for these subjects) should be reduced by the same number of dose levels and same percentage dose reduction as it was reduced to during cycle 6 (which is the twice weekly carfilzomib dosing). Dexamethasone will be administered at a dose of 20 mg once daily on days 1, 2, 8, 9, 15, 16, 22, and 23 cycles 1 through 6 and at a dose of 40 mg once daily on days 1, 8, 15 for the Kd arm for cycles 7 through 12 for these subjects.

All doses should be administered on the scheduled day  $\pm$  2 days, and the day 8 and 15 doses should have at least a 5-day treatment-free interval. The starting dose should be modified for chronic mild hepatic insufficiency per Section 7.1.1.2.1.

Table 7-1. Carfilzomib Dosage

Cycle 1	Cycle 2	Cycles 3-12		
Kd Arm				
D1, 2: 20 mg/m  D8, 9, 15, 16: 56 mg/m 	D 1, 2, 8, 9, 15, 16: 56 mg/m 	D1, 8, 15: 70 mg/m 		
KRd Arm	KRd Arm			
D1, 2: 20 mg/m  D8, 9, 15, 16: 27 mg/m 	D 1, 2, 8, 9, 15, 16: 27 mg/m 	D1, 8, 15: 56 mg/m 		
KPd Arm				
D1, 2: 20 mg/m  D8, 9, 15, 16: 27 mg/m 	D 1, 2, 8, 9, 15, 16: 27 mg/m 	D1, 8, 15: 56 mg/m 		

D = day

Subjects receiving carfilzomib at doses less than the protocol planned dose (56 mg/m^2 or 27 mg/m^2 based on treatment arm) during cycle 2 may have been reduced by 1 or more dose levels and/or by 25% for hepatic function abnormalities. Subjects should have the starting nominal dose of carfilzomib (70 mg/m^2 or 56 mg/m^2 based on treatment arm) on day 1 cycle 3 reduced by the same number of dose levels and the same

Protocol Number: 20170596

**Date**: 20 May 2019 Page 51 of 132

percentage dose reduction as they were reduced during cycle 2, see Table 7-2 for dose level reductions.

Carfilzomib is to be administered as an IV infusion over 30 (± 5) minutes. Subjects should receive 250 mL of normal saline or equivalent IV fluid prior to and after each dose during cycle 1. After cycle 1, at the discretion of treating physician, subjects may receive up to but no more than 250 mL of normal saline or equivalent fluid prior to each dose of carfilzomib. For subjects at risk of TLS, see Section 7.1.4.3.

Mechanical infusion pumps are recommended, but gravity-dependent infusions are permitted if the 30-minute infusion duration can be reliably maintained. Carfilzomib infusion must occur at a facility capable of managing hypersensitivity reactions.

Each subject's first dose will be calculated based upon baseline BSA per the Mosteller formula. In subjects with BSA of greater than  $2.2 \text{ m}^2$ , the dose should be capped based on a BSA of  $2.2 \text{ m}^2$ . The dose for each subject should not be revised unless the subject experiences a change in body weight of  $\geq 20\%$  compared to baseline or last calculation of BSA, in which case the BSA and dose should be recalculated. The dose can also be modified in response to toxicity following the dose modification guideline tables (see Section 7.4).

The planned dose, dose administered, start date/time, stop date/time, reason for change in planned dose or schedule, and package lot number of carfilzomib are to be recorded on each subject's CRF.

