**Date:** 20 May 2019 **Page 21 of 132** 

Table 2-1. Schedule of Activities

	Screening a b				Tre	eatr	nen	t P	erio	d				Safety	
	(up to			Су	cle	1-2				C	ycl	e 3-	12	FU c (30	
PROCEDURE	21 days before Day 1)	Day 1	2	8	9	15	16	22	23	1	8	15	21	[+3] days post last dose)	Notes
Bone Lesion Assessment b	х														Screening and will be repeated if worsening clinical symptoms suggest PD, or as clinically indicated. (see Section 12.8 for IMWG criteria)
Plasmacytoma evaluation b	х														See Section 9.2.2.3. Only required at screening in subjects if clinically suspected and to confirm response (if performed at screening, see Section 12.8 for IMWG criteria)
Bone marrow aspirate with FISH b	Х														Bone marrow aspirate is required at screening and to confirm a response of CR (see Section 12.8 for IMWG criteria). FISH is only required at screening.
CLINICAL OUTCOME ASSESSM	MENTS														
EORTC QLQ-C30		Х								Х				X	During treatment period, these
EORTC QLQ-MY20		Х								Х				Х	questionnaires must be completed on day 1 of each cycle prior to dosing.
Amgen Satisfaction and Convenience Questionnaire		x								x				Х	During treatment period, these questionnaires must be completed on day 1 of each cycle prior to dosing, starting with C2D1. Items 8-11 to be collected only once at end of treatment or at completion of the trial.

Page 4 of 7

**Protocol Number:** 20170596

**Date:** 20 May 2019 Page 22 of 132

Table 2-1. Schedule of Activities

	Screening a b				Tre	eatr	nen	t Pe	erio	d				Safety	
	(up to			Су	cle	1-2				С	ycl	e 3-′	12	FU c (30	
PROCEDURE	21 days before Day 1)	Day 1	2	8	9	15	16	22	23	1	8	15	21	[+3] days post last dose)	
STUDY TREATMENT															
Kd ARM															
Carfilzomib administration h		X	×	X	X	X	×			x	x	x			Cycle 1: 20 mg/m² on days 1 and 2; 56 mg/m² on days 8, 9, 15, and 16 Cycle 2: 56 mg/m² Cycles 3-12: 70 mg/m² For subjects with baseline hepatic function abnormalities (bilirubin or AST > ULN), see Section 7.1.1.2.1 for modification of the initial dose. For cycle 3, for subjects who were previously dose reduced, see Section 7.1.1.2 for starting dose.
Dexamethasone administration h		x	х	X	X	X	X	Xi	Xi	х	х	х			Cycles 1-2: 20 mg Cycles 3-12: 40 mg For subjects ≥ 75 years of age, see Section 7.4.1.2 for dose modification.

**Protocol Number:** 20170596

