# 7.1.2 Non-investigational Products

# 7.1.2.1 Dexamethasone: Dosage, Administration, and Schedule

For all treatment arms, dexamethasone will be taken orally or by IV infusion at a dose of 20 mg once-daily on days 1, 2, 8, 9, 15, 16, 22, and 23 of Kd cycles 1-2, and at a dose 40 mg once-daily on days 1, 8, 15 of Kd cycles 3-12. All doses should be administered on the scheduled days  $\pm$  2 days but prior to carfilzomib infusion except for days 22 and 23 of cycles 1-2.

Dexamethasone will be administered at least 30 minutes (but no more than 4 hours) prior to carfilzomib. Subjects receiving dexamethasone IV on days 1, 2, 8, 9, 15, and 16, may receive the day 22 and day 23 dose orally.

For subjects  $\geq$  75 years of age, see Section 7.4.1.2 for dose modification.

The dose, date, time, and reason for dose change are to be recorded on each subject's CRF.

Dexamethasone will not be provided or reimbursed by Amgen. The investigator will be responsible for obtaining supplies of dexamethasone.

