# 7.4.1.2 Non-Amgen/Amgen Non-investigational Product: Dexamethasone

The reason for dose change of dexamethasone is to be recorded on each subject's CRF.

For conditions that do not require dexamethasone dose reduction, refer to Section 7.4.1.1.3.

For subjects  $\geq$  75 years of age, the starting dose of dexamethasone should be 20 mg weekly, 10 mg administered on days 1, 2, 8, 9, 15, 16, 22, and 23 during cycles 1-2, and 20 mg administered on the days 1, 8, 15 during cycles 3-12.

<sup>a For a rapid fall from baseline in estimated GFR or an absolute fall of ≥ 60 mL/min/1.73 m², contact the medical monitor.

<sup>b In the event of a possible drug-related nonhematologic toxicity, the investigator should, to the best of his/her ability, assess its relationship to carfilzomib (K), dexamethasone (d), or the combination of Kd to the extent possible. If both carfilzomib and dexamethasone are considered likely to be involved, then recommended actions for both should be instituted.

Protocol Number: 20170596

**Date:** 20 May 2019 Page 63 of 132

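### For Kd subjects kept on six twice-weekly cycles, the age-75 dexamethasone rule and the mild-hepatic carfilzomib rule still switch at cycle 3

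*Protocol*

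**What the plan says.** Protocol Section 7.1.1.2 defines a carry-over group: Kd subjects who had completed more than 2 but fewer than 6 twice-weekly cycles when amendment 3 was implemented. "These subjects should complete the dosing regimen as per protocol amendment 2", which means six twice-weekly cycles and then once-weekly dosing from cycle 7. Their dexamethasone is given "at a dose of 20 mg once daily on days 1, 2, 8, 9, 15, 16, 22, and 23 cycles 1 through 6" and then "at a dose of 40 mg once daily on days 1, 8, 15 for the Kd arm for cycles 7 through 12". Neither clause mentions age. The same paragraph tells sites to run the Table 2-1 columns for cycles 1 and 2 through cycle 6, and the later columns from cycle 7. At cycle 7, carfilzomib takes the same number of reduction levels and the "same percentage dose reduction as it was reduced to during cycle 6".

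For subjects aged 75 or older, Section 7.4.1.2 sets "10 mg administered on days 1, 2, 8, 9, 15, 16, 22, and 23 during cycles 1-2" for the twice-weekly phase. For the once-weekly phase the rule changes to "20 mg administered on the days 1, 8, 15 during cycles 3-12". It has no separate line for the carry-over group. Two places lead there: the Kd dexamethasone row of Table 2-1 ("see Section 7.4.1.2 for dose modification") and Section 7.1.2.1 ("75 years of age, see Section 7.4.1.2 for dose modification").

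For mild hepatic insufficiency in the Kd arm, Section 7.1.1.2.1 gives 15 mg/m² on days 1 and 2 of cycle 1, 42 mg/m² for the rest of cycles 1 and 2, and 53 mg/m² in cycles 3 to 12. It too has no carry-over exception. Footnote b of Table 7-2 gives 42 mg/m² from day 8 of cycle 1 onward and states no later change.

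**The concern.** The carry-over subjects are still on the twice-weekly phase in cycles 3 to 6, but two special-population rules treat cycle 3 as the start of the once-weekly phase. A site that looks up an older or hepatically impaired carry-over subject by cycle number therefore finds a once-weekly dose for a subject on a twice-weekly schedule.

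For dexamethasone, the result is a lower cycle total and no dexamethasone on three carfilzomib days. Section 7.1.2.1 requires it at least 30 minutes before each infusion, and the infusion-reaction risk text in Section 3.3.3.1.8 relies on it. For carfilzomib, most of the hepatic reduction is lost. Separately, the carry-over dexamethasone sentence, read alone, would give a subject aged 75 or older the full adult dose. What is at stake is dosing safety in a few older or hepatically impaired subjects.

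**Working it through.** **The plan's own figures.** The hepatic doses are 25% reductions: 0.75 × 20 = 15, 0.75 × 56 = 42 and 0.75 × 70 = 52.5, stated as 53 mg/m². The age rule halves dexamethasone: 20 to 10 mg in the twice-weekly phase and 40 to 20 mg in the once-weekly phase. Both sets reproduce. The 53 mg/m² figure is thus a reduction of the once-weekly 70 mg/m², and the 20 mg on days 1, 8 and 15 is a reduction of the once-weekly 40 mg. Neither belongs to a twice-weekly cycle.

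**Dexamethasone per 28-day cycle, age 75 or older.** The twice-weekly phase has 8 dosing days and the once-weekly phase has 3.

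| Reading | Cycles 3-6 | Cycles 7-12 |
|---|---|---|
| Section 7.4.1.2 by cycle number | 3 × 20 = 60 mg | 3 × 20 = 60 mg |
| Section 7.1.1.2 carry-over sentence alone | 8 × 20 = 160 mg | 3 × 40 = 120 mg |
| Age rule moved to the 6+6 schedule | 8 × 10 = 80 mg | 3 × 20 = 60 mg |

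By cycle number, Section 7.4.1.2 is 60 − 80 = −20 mg per cycle (−25%) in cycles 3 to 6. It leaves days 2, 9 and 16 without dexamethasone although carfilzomib is infused then. It agrees with the moved rule in cycles 1-2 (8 × 10 = 80 mg) and in cycles 7-12, so its numbering conflicts only in cycles 3 to 6. The carry-over sentence alone gives 160/80 = 2 and 120/60 = 2 times the reduced dose.

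**Carfilzomib, mild hepatic insufficiency, cycles 3 to 6.** There are 6 infusions per cycle. By cycle number: 6 × 53 = 318 mg/m². At the twice-weekly reduced dose: 6 × 42 = 252 mg/m². The ratio is 53/42 = 1.262, or +26% per dose. Against the nominal 56 mg/m², the reduction shrinks from 25% to 1 − 53/56 = 5.4%.

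**How many cycles could be affected.** Counting whole cycles, a carry-over subject had completed 3, 4 or 5 when amendment 3 reached the site, which leaves 3, 2 or 1 twice-weekly cycles. From that point, the rules by cycle number would give 60, 40 or 20 mg less dexamethasone (20 mg per cycle). They would give 18, 12 or 6 infusions at 53 instead of 42 mg/m². A subject part-way through cycle 3 would add part of one more cycle. These counts are upper limits: implementation dates are not given, and the current version is dated 20 May 2019, against 29 March 2019 for amendment 3.

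**The case against.** The strongest reply is that the protocol already contains the answer. Section 7.1.1.2 carries the Table 2-1 content for cycles 1 and 2 through cycle 6, and the Kd dexamethasone row of that table points to the age rule. Read together, this gives 10 mg on 8 days through cycle 6 and 20 mg on days 1, 8 and 15 afterwards. The cycle-3 reading also contradicts the requirement in Section 7.1.2.1 that dexamethasone precede carfilzomib. For the hepatic dose, footnote b of Table 7-2 and the percentage carry-over at cycle 7 point to 42 and then about 53 mg/m². Finally, these subjects follow amendment 2, and its dosing text is not among the documents.

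Most of this stands: the intended doses can be recovered. It does not remove the inconsistency. The mapping covers the schedule of activities and does not renumber Sections 7.4.1.2 or 7.1.1.2.1, so the age pointer still ends at a rule that changes at cycle 3. Section 7.1.1.2 also sends mild-hepatic subjects to Section 7.1.1.2.1 immediately after the carry-over paragraph, and that section changes at cycle 3 as well.

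A reader might infer from the carry-over sentence that the protocol withdraws the age reduction for this group and prescribes the doubled dose. The documents do not support that. The synopsis and Section 7.1.2.1 state the 20 and 40 mg doses in the same way and leave the age exception to Section 7.4.1.2. The pointers cover all arms, and nothing exempts carry-over subjects. The doubling is what a site would give if it read one sentence in isolation.

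**Conclusion.** The inconsistency is real and minor. In the current (amendment 4) wording, two special-population dosing rules were not renumbered for Kd subjects on the 6+6 schedule. Applied by cycle number in cycles 3 to 6, they give 60 instead of 80 mg of dexamethasone per cycle for age 75 or older, and 53 instead of 42 mg/m² of carfilzomib twice weekly for mild hepatic insufficiency. The hepatic part is the better covered of the two, because two other provisions already indicate the right dose.

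The conclusion assumes that the age and hepatic rules are meant to follow the dosing phase and not the cycle number, as the Table 2-1 mapping, footnote b and the cycle 7 carry-over indicate. The amendment 2 dosing text could not be checked. The group is closed. Its size, and the number aged 75 or older or with mild hepatic insufficiency, are not given and may be zero.

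A reader might also infer that the primary dose-intensity endpoints are distorted, or that a definite number of doses was still affected on 20 May 2019. Neither can be shown. The number of affected subjects is unknown, and Appendix 3 (Section 12.3) makes implementation at each site depend on IRB approval, so the dates differ by site. No effect on an endpoint, the sample size or the analysis is claimed.

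**What to change.** Add one sentence to the carry-over paragraph of Section 7.1.1.2, or send a site memo. It should say that for these subjects references to cycles 1-2 in Sections 7.1.1.2.1 and 7.4.1.2 mean cycles 1-6, that references to cycles 3-12 mean cycles 7-12, and that the dexamethasone reduction for age 75 or older applies throughout. Before issuing it, the sponsor should check it against the amendment 2 dosing text and confirm whether any affected subject is still on treatment. The cost is one sentence or memo, with no change to design, sample size or analysis.

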## 7.1.1.2.1 Starting Dose in Hepatic Insufficiency

For subjects with mild hepatic insufficiency during screening, the initial dose of carfilzomib on days 1 and 2 of cycle 1 should be reduced by 25% to 15 mg/m². For subjects in the Kd arm, starting on day 8 and for all subsequent doses of carfilzomib during cycles 1 and 2, the dose should be 42 mg/m² (Brown et al, 2017); the dose in cycle 3 through 12 should be 53 mg/m². For subjects in the KRd and KPd arms, starting on day 8 and for all subsequent doses of carfilzomib during cycles 1 and 2, the dose should be 20 mg/m² as per the protocol and doses in cycles 3 through 12 should be 42 mg/m².

If hepatic function returns to normal, the dose in following cycles may be re-escalated to the full dose per the protocol. For dose modification due to subsequent changes in hepatic function, refer to Section 7.4.1.1.3 (Table 7-4).

Protocol Number: 20170596

**Date:** 20 May 2019 Page 52 of 132

Mild and moderate hepatic dysfunction is defined as:

Mild: bilirubin > 1.0-1.5 x ULN, or AST > ULN with bilirubin ≤ ULN

Moderate: bilirubin > 1.5-3.0 x ULN with any AST

Grade 3 elevation in ALT and/or AST (> 5x ULN)

# 7.1.2 Non-investigational Products

# 7.1.2.1 Dexamethasone: Dosage, Administration, and Schedule

For all treatment arms, dexamethasone will be taken orally or by IV infusion at a dose of 20 mg once-daily on days 1, 2, 8, 9, 15, 16, 22, and 23 of Kd cycles 1-2, and at a dose 40 mg once-daily on days 1, 8, 15 of Kd cycles 3-12. All doses should be administered on the scheduled days  $\pm$  2 days but prior to carfilzomib infusion except for days 22 and 23 of cycles 1-2.

Dexamethasone will be administered at least 30 minutes (but no more than 4 hours) prior to carfilzomib. Subjects receiving dexamethasone IV on days 1, 2, 8, 9, 15, and 16, may receive the day 22 and day 23 dose orally.

For subjects  $\geq$  75 years of age, see Section 7.4.1.2 for dose modification.

The dose, date, time, and reason for dose change are to be recorded on each subject's CRF.

Dexamethasone will not be provided or reimbursed by Amgen. The investigator will be responsible for obtaining supplies of dexamethasone.

# 7.1.2.2 Lenalidomide

## 7.1.2.2.1 Prescribing Requirements

Lenalidomide, a non-Amgen non-investigational product, will also be used in this study for the KRd treatment arm. Lenalidomide should be administered in accordance with the REVLIMID REMS® program of Celgene Corporation (http://www.revlimidrems.com/.) All physicians who prescribe lenalidomide for research subjects assigned to the KRd arm of this study, and all research subjects enrolled on this study who are assigned to the KRd arm, must be registered in and comply with all requirements of the REVLIMID REMS® program.

Females of childbearing potential (FCBP) must agree to monitoring for pregnancy. In addition, males and FCBP are subject to certain restrictions as detailed in Section 12.5 while receiving lenalidomide.

Protocol Number: 20170596

**Date:** 20 May 2019 Page 53 of 132

